### **STROKE/CEREBROVASCULAR ACCIDENT and TIA**

Cerebrovascular Accident (Stroke) is defined as an acute episode of focal or global neurological dysfunction caused by brain, spinal cord, or retinal vascular injury as a result of hemorrhage or infarction. Stroke may be classified as ischemic or hemorrhagic with appropriate sub-definitions or as undetermined if there is insufficient information to allow categorization as ischemic or hemorrhagic.

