**TRILUMINATE Pivotal CIP**  
(Version F)

An entity closely related to ischemic stroke is transient ischemic attack (TIA). TIA is defined as a transient episode of focal neurological dysfunction caused by brain, spinal cord, or retinal ischemia, without acute infarction. The difference between TIA and ischemic stroke is the presence of infarction. In the absence of affirmative evidence confirming the presence or absence of infarction, a symptom duration of 24 hours will be used to distinguish TIA from ischemic stroke. By definition, TIA does not produce lasting disability.

The assessment of disability resulting from the stroke will be performed by the modified Rankin Scale (mRS). Assessment of the mRS is only required at scheduled visits through 24 months after onset of stroke, if stroke occurred. This approach will maximize the detection of new strokes, assist in ongoing evaluation of events previously determined to be TIAs, and provide an accepted and reliable indicator of the long-term impact of a given stroke. A disabling stroke is one that results (at 90 days after stroke onset) in an mRS score of 2 or more and in an increase of at least one mRS category from the individual's pre-stroke baseline. A non-disabling stroke is one that results (at 90 days after stroke onset) in an mRS score of less than 2 or that does not result in an increase of at least one mRS category from an individual's pre-stroke baseline.

Although imaging (typically, MRI for acute and chronic ischemia and haemorrhage, and CT for acute and chronic haemorrhage and chronic ischemia) is often used to supplement the clinical diagnosis of stroke, a diagnosis of stroke may be made on clinical grounds alone.

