**Diagnostic criteria**

Acute episode of a focal or global neurological deficit with at least one of the following: change in level of consciousness, hemiplegia, hemiparesis, numbness or sensory loss affecting one side of the body, dysphasia or aphasia, hemianopia, amaurosis fugax, or other neurological signs or symptoms consistent with stroke

Stroke – Duration of a focal or global neurological deficit  $\geq 24$  h; OR  $< 24$  h if available neuroimaging documents a new hemorrhage or infarct; OR the neurological deficit results in death

TIA – Duration of a focal or global neurological deficit  $< 24$  h, any variable neuroimaging does not demonstrate a new hemorrhage or infarct

No other readily identifiable non-stroke cause for the clinical presentation (e.g. brain tumor, trauma, infection, hypoglycemia, peripheral lesion, pharmacological influences), to be determined by or in conjunction with designated neurologist\*

Confirmation of the diagnosis by at least one of the following:

- Neurologist or neurosurgical specialist
- Neuroimaging procedure (CT scan or brain MRI), but stroke may be diagnosed on clinical grounds alone

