**Stroke classification**

Ischemic – An acute episode of focal cerebral, spinal, or retinal dysfunction caused by infarction of central nervous system tissue.

Hemorrhagic – An acute episode of focal or global cerebral or spinal dysfunction caused by intraparenchymal, intraventricular, or subarachnoid hemorrhage.

Undetermined – An acute episode where there is insufficient information to allow categorization as ischemic or hemorrhagic.

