**Stroke definitions†**

Disabling stroke – a mRS score of 2 or more at 90 days and an increase of at least one mRS category from an individual's pre-stroke baseline

Non-disabling stroke – a mRS score of less than 2 at 90 days or one that does not result in an increase of at least one mRS category from an individual's pre-stroke baseline

\*Patients with non-focal global encephalopathy will not be reported as a stroke without unequivocal evidence of cerebral infarction based upon neuroimaging studies (CT scan or Brain MRI).

†Modified Rankin Scale assessments should be made by qualified individuals according to a certification process.

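### The encephalopathy footnote to the stroke definition recognises only infarction, so an imaging-proven bleed presenting as encephalopathy is a stroke in one part of Appendix II and not in another

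*Protocol*

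**What the plan says.** All the relevant text is in Protocol Appendix II, under the entry for stroke, cerebrovascular accident and TIA.

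- **General definition.** Stroke is an "acute episode of focal or global neurological dysfunction caused by brain, spinal cord, or retinal vascular injury as a result of hemorrhage", and the sentence goes on to name infarction as the alternative cause.
- **Diagnostic criteria.** The deficit may be focal or global, and a change in level of consciousness is a listed sign. A deficit shorter than 24 hours still qualifies "if available neuroimaging documents a new hemorrhage or infarct". A separate criterion, that no other non-stroke cause is readily identifiable, is "to be determined by or in conjunction with designated neurologist". The asterisk for the footnote is attached to that criterion.
- **Stroke classification.** The haemorrhagic class is "An acute episode of focal or global cerebral or spinal dysfunction caused by intraparenchymal, intraventricular, or subarachnoid hemorrhage". The ischaemic class is "An acute episode of focal cerebral, spinal, or retinal dysfunction caused by infarction of central nervous system tissue".
- **Footnote (under Stroke definitions).** "Patients with non-focal global encephalopathy will not be reported as a stroke without unequivocal evidence of cerebral infarction based upon neuroimaging studies", with CT and brain MRI given as the studies meant.

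The modified Rankin Scale (mRS) is required only at visits after a stroke (Section 7.15, Table 1, footnote f; repeated in the Appendix II stroke entry). The disabling or non-disabling label depends on the mRS at 90 days.

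**The concern.** The footnote is an instruction on what is reported as stroke, and it names one kind of imaging evidence where the criteria and the classification name two. An adjudicator with a confused or comatose subject and a subarachnoid bleed on CT has two instructions that cannot both be followed.

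The event label is at stake, and so is the data collection that the label triggers. If the event is not called a stroke, the mRS may never be taken, and whether the event was disabling may not be recoverable later.

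**Working it through.** The plan states no figure for this point, so there is none to reproduce. The check compares the texts and then gives a rough size.

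**Test case.** A subject has a non-focal global encephalopathy, a new intraparenchymal, intraventricular or subarachnoid haemorrhage on CT or MRI, and no infarct.

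| Text in Appendix II | What it asks for | Result for the test case |
|---|---|---|
| General definition | Focal or global dysfunction; haemorrhage or infarction | Stroke |
| Diagnostic criteria | Focal or global deficit; lasting 24 h or more, or shorter with new haemorrhage or infarct on imaging, or fatal | Stroke |
| Classification, haemorrhagic | Focal or global dysfunction from one of the three bleed types | Haemorrhagic stroke |
| Footnote | For non-focal global encephalopathy, unequivocal imaging evidence of infarction | Not reported as stroke |

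Three texts agree and the fourth contradicts them. No other sentence in the appendix exempts haemorrhage from the footnote.

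There is a related oddity. The only route that the footnote leaves open for an encephalopathy is infarction, yet the ischaemic class is limited to focal dysfunction. It is the haemorrhagic class that admits global dysfunction.

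**Reach.** Stroke does not appear in the primary endpoint (Section 5.1.1), the powered secondary endpoints (5.1.2), the major adverse event composite (Appendix II) or the descriptive endpoints (5.1.3), nor in the single-arm lists (5.2). No power or type I error figure depends on it.

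**Rough size.** About 225 subjects are expected in the Device group (450 randomized 1:1). The three shares below are assumptions, because the documents give none:

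- Strokes at 1% to 3%: 225 × 0.01 = 2.25; 225 × 0.03 = 6.75.
- Of these, 10% to 30% haemorrhagic: 2.25 × 0.10 = 0.225; 6.75 × 0.30 = 2.025.
- Of these, 10% to 40% presenting as non-focal encephalopathy: 0.225 × 0.10 ≈ 0.02; 2.025 × 0.40 ≈ 0.8.

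This gives about 0.02 to 0.8 misclassified events per 225 subjects. Applying the same assumptions to all 450 doubles the range to about 0.05 to 1.6.

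**The case against.** The strongest reply is that the footnote is attached to the criterion that rules out non-stroke causes, a judgement made with a neurologist. On that reading it exists to keep metabolic or toxic encephalopathy out of the stroke count, and a subject with a bleed on imaging already has an identified stroke cause. This is probably the intent. But the words set a reporting condition that only infarction satisfies, so the conflict remains in the text.

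Two further points stand and limit the concern. The footnote covers non-focal global encephalopathy, which is narrower than every global presentation. And the bleed is not lost: intracranial haemorrhage is Type 3c major bleeding in Appendix II, and a fatal case counts as a death in the primary endpoint.

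A reader might also infer four stronger things that the documents do not support:

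- *That every haemorrhagic stroke with a global presentation is excluded.* A global deficit that is not an encephalopathy falls outside the footnote.
- *That the under-count favours the Device arm.* Procedural anticoagulation (Section 7.6.2.7) is confined to subjects who undergo the procedure. For subjects already on oral anticoagulants, however, Section 7.8.1.2 mainly resumes existing treatment, and Control subjects may take the same drugs. The direction is speculative.
- *That stroke counts by arm are certain to be affected through SAP Section 3.2.* The by-group summary there covers CEC-adjudicated events. The documents name cause of death, heart failure hospitalization and major adverse event components as examples, and leave the full list to the CEC charter, which is not among them.
- *That the TIA text creates a second contradiction.* The sentence "The difference between TIA and ischemic stroke is the presence of infarction" could suggest that a deficit of 24 hours or more with infarction excluded is a TIA. But the same paragraph defines TIA as transient, and the diagnostic criteria confine it to under 24 hours.

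**Conclusion.** The contradiction is real but minor. Read literally, the footnote denies the label of stroke to an encephalopathic subject with an imaging-proven bleed and no infarct, whereas the general definition, the diagnostic criteria and the classification all give it. The mRS for that event may be missed as a result.

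The effect is limited to stroke safety classification, and is probably under one event per 225 subjects. That size rests wholly on the assumed stroke rate, haemorrhagic share and encephalopathic share. The contradiction itself rests only on the text. No endpoint, power or error rate changes, and no bias between the arms is shown.

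**What to change.** In the footnote, replace *cerebral infarction* with *cerebral infarction or intraparenchymal, intraventricular or subarachnoid hemorrhage*. This keeps the demand for unequivocal imaging proof, so metabolic and toxic encephalopathy stay out, and it matches the list in the haemorrhagic class. A broader term such as intracranial hemorrhage would not match, because it would also let in bleeds, for example subdural, that the classification does not list.

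Carry the same wording into the definitions that the CEC uses. The same edit is a convenient place to settle whether a global presentation with infarction belongs in the ischaemic class, which is now limited to focal dysfunction.

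The cost is a few words in Appendix II and in the CEC definitions. The only added data are mRS assessments for any subject newly classed as having a stroke. The reported stroke count could rise slightly.

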**SYMPTOMATIC TRICUSPID REGURGITATION**

Symptomatic refers to limitation of physical activity (i.e. NYHA Classification II, III or IV)

**TRICUSPID VALVE STENOSIS**

Defined as a tricuspid valve orifice of  $\leq 1.0 \text{ cm}^2$  and/or mean gradient  $\geq 5 \text{ mmHg}$  as measured by the Echocardiography Core Laboratory. Other parameters (PHT  $\geq 190 \text{ msec}$  or CW TV VTI  $>60 \text{ cm}$ ) may also suggest significant tricuspid stenosis.

**TRICUSPID REGURGITATION SEVERITY**

TR grading will be based on a 5-point scale: mild (1), moderate (2), severe (3, 4, 5). Mild, moderate, and severe will be graded based on the 2017 ASE Guidelines (Zoghbi 2017). Further stratification of severe into 3, 4 and 5 have been developed by the Echo Scientific Committee to provide further granularity in the range beyond severe. See Appendix XII for further grading information.

**TRILUMINATE Pivotal CIP**  
(Version F)

**TRILUMINATE Pivotal CIP**  
(Version F)

21 APPENDIX V: RATES OF FORSEEABLE ADVERSE EVENTS

[REDACTED]

[REDACTED]

[REDACTED]	[REDACTED]	[REDACTED]	[REDACTED]	[REDACTED]	[REDACTED]
[REDACTED]	[REDACTED]	[REDACTED]	[REDACTED]	[REDACTED]	[REDACTED]
[REDACTED]			[REDACTED]		
[REDACTED]	[REDACTED]				
[REDACTED]			[REDACTED]		[REDACTED]
[REDACTED]		[REDACTED]			
[REDACTED]		[REDACTED]			
[REDACTED]			[REDACTED]		
[REDACTED]					[REDACTED]

TRILUMINATE Pivotal CIP  
(Version F)

[REDACTED]	[REDACTED]	[REDACTED]			
[REDACTED]		[REDACTED]			
[REDACTED]	[REDACTED]	[REDACTED]			
[REDACTED]	[REDACTED]	[REDACTED]			
[REDACTED]		[REDACTED]		[REDACTED]	
[REDACTED]	[REDACTED]				
[REDACTED]	[REDACTED]	[REDACTED]			
[REDACTED]	[REDACTED]	[REDACTED]			
[REDACTED]	[REDACTED]	[REDACTED]			
[REDACTED]	[REDACTED]	[REDACTED]			
[REDACTED]	[REDACTED]	[REDACTED]			
[REDACTED]	[REDACTED]	[REDACTED]			
[REDACTED]	[REDACTED]	[REDACTED]			
[REDACTED]	[REDACTED]	[REDACTED]			
[REDACTED]	[REDACTED]	[REDACTED]	[REDACTED]		
[REDACTED]	[REDACTED]	[REDACTED]	[REDACTED]		
[REDACTED]	[REDACTED]	[REDACTED]	[REDACTED]		

**TRILUMINATE Pivotal CIP**  
(Version F)

22 APPENDIX VI: LABELS

TRILUMINATE Pivotal CIP  
(Version F)

23 APPENDIX VII: CASE REPORT FORMS

**TRILUMINATE Pivotal CIP**  
(Version F)

25 APPENDIX IX: MONITORING PLAN

26 APPENDIX X: Transthoracic Echo (TTE) Protocol

[REDACTED]

[REDACTED]

[REDACTED]

[REDACTED]

[REDACTED]

TRILUMINATE Pivotal CIP  
(Version F)

[REDACTED]

TRILUMINATE Pivotal CIP  
(Version F)

[REDACTED]

TRILUMINATE Pivotal CIP  
(Version F)

[REDACTED]

[REDACTED]

[REDACTED]

[REDACTED]

TRILUMINATE Pivotal CIP  
(Version F)

[REDACTED]

[REDACTED]

[REDACTED]

[REDACTED]

TRILUMINATE Pivotal CIP  
(Version F)

27 APPENDIX XI: Transesophageal Echo (TEE) Protocol

[REDACTED]

[figure not shown]
TRILUMINATE Pivotal CIP  
(Version F)

[Redacted]

[Redacted]

[Redacted]

**TRILUMINATE Pivotal CIP**  
(Version F)

TRILUMINATE Pivotal CIP  
(Version F)

[REDACTED]

[REDACTED]

[REDACTED]

[REDACTED]

[REDACTED]

TRILUMINATE Pivotal CIP  
(Version F)

[figure not shown]
[REDACTED]

TRILUMINATE Pivotal CIP  
(Version F)

28 APPENDIX XII: ECHOCARDIOGRAPHY TR GRADING

**TRILUMINATE Pivotal CIP**  
(Version F)

Study Document No: ABT-CIP-10249

Study Name: TRILUMINATE Pivotal

[figure not shown]
**CONFIDENTIAL:** May not be reproduced outside of Abbott without written permission from Document Control. This is a quality record which will be retained per the local retention policy.

**TRILUMINATE Pivotal CIP**  
(Version F)

**29 APPENDIX XIII: SIX MINUTE WALK TEST GUIDELINES – AMERICAN THORACIC SOCIETY**

[figure not shown]

**TRILUMINATE Pivotal CIP**  
(Version F)

[figure not shown]

[figure not shown]
**TRILUMINATE Pivotal CIP**  
(Version F)

**TRILUMINATE Pivotal CIP**  
(Version F)

**TRILUMINATE Pivotal CIP**  
(Version F)

[figure not shown]

Study Document No: ABT-CIP-10249

[figure not shown]
Study Name: TRILUMINATE Pivotal

**CONFIDENTIAL:** May not be reproduced outside of Abbott without written permission from Document Control. This is a quality record which will be retained per the local retention policy.

[figure not shown]
**TRILUMINATE Pivotal CIP**  
(Version F)

**TRILUMINATE Pivotal CIP**  
(Version F)

**TRILUMINATE Pivotal CIP**  
(Version F)

30 APPENDIX XIV: Monitoring Exposure to Ionizing Radiation

(1) Implanting Investigator Training

[REDACTED]

[REDACTED]

[REDACTED]

[REDACTED]

[figure not shown]
[REDACTED]

[REDACTED]

[figure not shown]
[REDACTED]

[REDACTED]

**TRILUMINATE Pivotal CIP**  
(Version F)

**(1) Acute Evaluation**

**31 APPENDIX XV: Exceptions from ISO 14155 compliance**

Minimal exceptions to ISO 14155:2020 compliance are expected, though these exceptions do not affect the safety and protection of the clinical investigation subjects and do not compromise data quality and security.

- This clinical investigation provides market approved devices in the EU, which will be used within their intended purpose, thus clinical investigation labelling will not be applied, a separate investigator Brochure will not be created, and clinical device accountability will not be set up.

**TRILUMINATE Pivotal CIP**  
(Version F)

- The study will not be submitted for review to the Competent Authority, only standard vigilance reporting will be observed. Local and/or regional requirements might be still applicable and will be tracked in a study specific Safety Plan.
- Financial disclosures will not be collected from the Investigators.
- separate study risk assessment will not be applied, the applicable risks are described and communicated in the current Clinical Investigational Plan and IFUs for the medical devices under investigation

TRILUMINATE Pivotal CIP  
(Version F)

[REDACTED]

[REDACTED]

[figure not shown]
[REDACTED]

[REDACTED]

[REDACTED]

[REDACTED]

### 32.6 Schedule of Events

a If performed within 14 days of assessment for screening, then screening can be used for baseline.

Study Document No: ABT-CIP-10249

Study Name: TRILUMINATE Pivotal

**CONFIDENTIAL:** May not be reproduced outside of Abbott without written permission from Document Control. This is a quality record which will be retained per the local retention policy.

TRILUMINATE Pivotal CIP  
(Version F)

[REDACTED]

[REDACTED]

[REDACTED]

[REDACTED]

[REDACTED]

[REDACTED]

[REDACTED]

[REDACTED]

[REDACTED]

TRILUMINATE Pivotal CIP  
(Version F)

33 APPENDIX XVII: REVISION HISTORY

Version	Date	Details	Rationale
[REDACTED]	[REDACTED]	[REDACTED]	[REDACTED]
[REDACTED]	[REDACTED]	[REDACTED]	[REDACTED]
[REDACTED]	[REDACTED]	[REDACTED]	[REDACTED]
[REDACTED]	[REDACTED]	[REDACTED]	[REDACTED]
[REDACTED]	[REDACTED]	[REDACTED]	[REDACTED]
[REDACTED]	[REDACTED]	[REDACTED]	[REDACTED]

1.0 SYNOPSIS OF STUDY DESIGN

1.1 Purpose of the Statistical Analysis Plan

This statistical analysis plan (SAP) is to provide a detailed and comprehensive description of the planned methodology and analysis to be used for ABT-CIP-10249, the TRILUMINATE PIVOTAL clinical investigation. This plan is based on the Version F of Clinical Investigation Plan.

1.2 Clinical Investigation Objectives

The objective of this trial is to evaluate the safety and effectiveness of the TriClip™ device in improving clinical outcomes in symptomatic patients with severe tricuspid regurgitation (TR) who have been determined by the site's local heart team to be at intermediate or greater estimated risk for mortality or morbidity with tricuspid valve surgery.

1.3 Clinical Investigation Design

TRILUMINATE Pivotal trial is a prospective, multicenter, randomized, controlled, clinical trial of the TriClip™ device in symptomatic subjects with severe TR, who have been determined by the site's local heart team to be at intermediate or greater estimated risk of mortality or morbidity with tricuspid valve surgery.

The trial consists of two cohorts: Randomized cohort and Single-arm cohort. Determination as to whether a patient is placed in the Randomized cohort or Single-arm cohort will be made by the independent eligibility committee. Patients will be placed in the Single-arm cohort if they meet the following criteria:

- The likelihood of achieving TR reduction of at least 1 grade (as assessed using a 5-grade scale) is high, and
- The likelihood of achieving TR reduction to moderate or less (≤ 2) is low

All other patients will be randomized.

Randomization will occur in a minimum of 350 eligible subjects in a 1:1 ratio to receive either the TriClip™ device or medical therapy (control group), at up to 80 sites as follows:

- **TriClip™ Device (Device) Group:** Eligible subjects will undergo the TriClip procedure and will continue to be managed on medical therapy, per physician discretion.
- **Medical Therapy (Control) Group:** Eligible subjects will not undergo the TriClip procedure but will continue to be managed on medical therapy, per physician discretion.

The Single-arm cohort will enroll approximately 200 eligible subjects and all subjects will receive the TriClip™ device.

Statistical Analysis Plan

Additionally, up to 3 roll-in subjects will be permitted per implanter without prior experience of transcatheter treatment of the tricuspid valve. The trial will be conducted in US, Canada and Europe, with a minimum of 50% of the subjects in each cohort enrolled in the US.

Following the completion of enrollment of the TRILUMINATE Pivotal trial, subjects from eligible sites will be enrolled into a continued access study (CAS). Details of the analysis plan to continued access study is included in Appendix B.

An independent Clinical Events Committee (CEC) will adjudicate events including cause of death, HF hospitalization and components of major adverse events. The independent ECL will assess echocardiographic endpoints.

1.4 Endpoints

1.4.1 Endpoints – Randomized Cohort

1.4.1.1 Primary Endpoint – Randomized Cohort

The primary endpoint is a hierarchical composite of all-cause mortality or tricuspid valve (TV) surgery, heart failure hospitalizations, and quality of life improvement assessed using the Kansas City Cardiomyopathy Questionnaire (KCCQ) at 12 months. The endpoint will be evaluated in a hierarchical order as follows:

- Time to all-cause death or TV surgery
- Number of Heart Failure (HF) Hospitalizations
- An Improvement of ≥ 15 points in KCCQ from baseline

The primary endpoint must be met for study success.

[REDACTED]

1.4.1.2 Secondary Endpoints – Randomized Cohort

The following secondary endpoints will be assessed at the same time of the primary endpoint for labeling claims:

- TR Reduction to moderate or less at 30-day visit post procedure. The endpoint will be assessed as the proportion of subjects who have moderate or less TR at 30 days.

Statistical Analysis Plan

- Freedom from major adverse events (MAE) occurring after procedure attempt (femoral vein puncture) at 30 days. Components of MAE consist of the following:
 - Cardiovascular Mortality,
 - New Onset Renal Failure,
 - Endocarditis Requiring Surgery, and
 - Non-Elective Cardiovascular Surgery for TriClip™ device-related AE post-index procedure.
- Change in KCCQ at 12 months
- Change in 6MWT at 12 months

The following secondary endpoints will be assessed after all randomized subjects complete 24-month follow-up:

- Recurrent HF hospitalizations at 24 months
- Freedom from all-cause mortality, tricuspid valve surgery and tricuspid valve intervention at 24 months

